3.3.2 SL-172154 Administered with MIRV

Subjects with platinum-resistant ovarian, primary peritoneal, or fallopian tube cancer whose tumors are positive for FR α expression (PS2+ \geq 25%) as defined by the Ventana FOLR1 Assay will be enrolled to receive SL-172154 and MIRV at the dose identified in the dose escalation part of the study. Premedication as prophylaxis for IRR with dexamethasone (8 mg IV), an antipyretic and antihistamines should be administered at least 30 minutes prior to each SL-172154 administration as described in Section 5.1.1. In addition, premedication as prophylaxis for IRR with antipyretic, antihistamines, and dexamethasone should be administered at least 30 minutes prior to each MIRV administration as described in Section 5.3.2.1.

Approximately 64 subjects will be enrolled in the MIRV dose expansion cohort. Approximately 70 subjects will be enrolled in this MIRV cohort which is anticipated to include approximately 20 subjects at the potential SL-172154 RP2D in either dose escalation or dose expansion for each of the following three tumor FR α expression subgroups: high (PS2+ \geq 75%), medium (PS2+ \geq 50% and $<$ 75%), and low (PS2+ \geq 25% and $<$ 50%). This estimation is based on the anticipated frequency of patients with high grade serous ovarian cancer who fall into each of these FR α expression subgroups. If this distribution is not achieved in any subgroup, approximately 10 additional subjects may be enrolled in this dose expansion cohort in order to achieve these subject numbers. Treatment will be administered in 21-day cycles until at least one of the study treatment discontinuation criteria is met (Section 3.1.1). Alternate dose level(s) or treatment schedule(s) may be evaluated at the discretion of the Sponsor based on emerging clinical or nonclinical data in the SL-172154 program.

3.4 Selection of Recommended Phase 2 Dose

If an MTD is not observed, the MAD would then be the highest dose of SL-172154 administered as specified in the protocol. Selection of the recommended dose for SL-172154 for further study in combination with PLD and in combination with MIRV will be based upon the totality of the safety, tolerability, PK, PD, and efficacy data in subjects treated with each of the regimens in dose escalation and dose expansion cohorts. The RP2D is a dose of SL-172154 that can be safely administered with standard of care doses of PLD or with the recommended dose of MIRV. In addition, preliminary efficacy of each of the combination regimens will be assessed to determine whether either or both of the regimens warrant further evaluation in a Phase 2 study.

3.5 Definition of Dose-Limiting Toxicity

Protocol-defined DLT criteria are applicable to the dose escalation portion of the study. The determinant period for DLT is the first cycle of treatment (i.e., 28 days for PLD cohorts, 21 days for MIRV cohorts); however, there is provision in the criteria below for AEs that occur beyond this period to be considered in the determination of the RP2D. All toxicities except for CRS and ocular AEs will be graded as per NCI CTCAE v5. CRS will be graded per the American Society for Transplantation and Cellular Therapy (ASTCT) Consensus Grading Criteria for CRS (described in Section 3.7.1.2); ocular AEs for the MIRV cohort will be graded per the tables provided in the Appendix Section 16.6. AEs clearly related to the underlying disease, disease progression, intercurrent illness, or concomitant medications are not considered DLTs. AEs that are clearly related to PLD or MIRV only do not have to be considered DLTs, unless the investigator considers the AE to be exacerbated by SL-172154. DLT is defined as an event considered related or possibly related to SL-172154 and meets one of the following criteria:

- Any death not clearly related to underlying disease or intercurrent illness
- Elevations in liver transaminases (aspartate aminotransferase [AST], alanine aminotransferase [ALT]) or total bilirubin:
 - In subject who enroll with AST/ALT/total bilirubin \leq upper limit of normal (ULN), AST or ALT elevation of $> 8x$ ULN **or** total bilirubin $> 5x$ ULN.
 - In subjects who enroll with AST/ALT/total bilirubin $>$ ULN, AST or ALT elevation of $> 8x$ baseline **or** total bilirubin $> 5x$ baseline.
 - Evidence of Hy's Law (AST or ALT $> 3x$ ULN [or baseline*] with concurrent increase in total bilirubin $> 2x$ ULN [*or baseline] without evidence of cholestasis or alternative explanation such as disease progression or viral hepatitis.

**ULN or baseline dependent on value at enrollment as described above.*

- Any AE that requires permanent discontinuation of SL-172154
- Any Grade 3 or greater AE except for those listed below:
 - Grade 3 fatigue lasting ≤ 7 days
 - Grade 3 anemia
 - Grade 3 or 4 neutropenia not associated with fever (temperature $> 38.5^{\circ}\text{C}$) that improves to Grade 2 within 7 days
 - Grade 3 or 4 lymphopenia
 - Grade 3 thrombocytopenia not associated with clinically significant bleeding and does not require medical intervention
 - Grade 3 anorexia, nausea, vomiting, or diarrhea, provided that it does not require tube feeding, total parenteral nutrition, or require or prolong hospitalization
 - Grade 3 laboratory abnormalities which resolve to Grade 1 or baseline within 72 hours with or without intervention
 - Grade 3 hypertension that can be controlled (i.e., systolic BP < 140 mmHg and diastolic BP < 90 mmHg) with medical therapy
 - Grade 3 or 4 amylase and/or lipase abnormalities that are not associated with clinical signs/symptoms or finding on imaging consistent with pancreatitis
 - Grade 3 endocrine disorder (thyroid, pituitary, hyperglycemia and/or adrenal insufficiency) that is managed with treatment with resolution of symptoms within 14 days after treatment onset
 - Vitiligo or alopecia of any grade

Other toxicities may be considered a DLT as determined by the investigator in conjunction with the SMC.

3.6 Concomitant Medications, Treatments, and Procedures

Investigators may prescribe concomitant medications or treatments deemed necessary to provide supportive care except for prohibited medications (Section 3.6.1). Best supportive care should be

provided (including antibiotics, bisphosphonates, receptor activator of nuclear factor kappa B ligand (RANKL) inhibitors, nutritional support, correction of metabolic disorders, hydration, optimal symptom control, and pain management including palliative radiotherapy) for all subjects when clinically indicated. The Medical Monitor should be consulted prior to starting palliative radiotherapy and prior to restarting study treatment after the completion of radiotherapy.

Subjects receiving recombinant erythropoietin (EPO) or darbepoetin- α before study start may continue to receive pretreatment doses. Primary prophylactic use of erythropoietic and granulocyte growth factors initiated during the first cycle of therapy is not permitted. In subsequent cycles, the use of erythropoietic and granulocyte growth factors in accordance with American Society of Clinical Oncology (ASCO) guidelines may be implemented at the discretion of the investigator.

Use of anticoagulant agents is allowed as clinically indicated.

Use of intranasal, inhaled, topical, injected (e.g., intra-articular injection) or local steroid or immunosuppressive medication is permitted. Temporary use of systemic corticosteroids (e.g., prior to computed tomography [CT] to prevent contrast allergies, premedication prior to each dose of MIRV administration) is acceptable.

Primary prophylaxis of nausea and vomiting using all agents except a steroid is permitted for PLD according to institutional guidelines.

For subjects enrolled in a MIRV cohort, an antiemetic (e.g., 5-HT3 serotonin receptor antagonists such as palonosetron, granisetron, or ondansetron) medication is recommended before each MIRV dose; additional antiemetics and/or antidiarrheal (e.g., loperamide) medications may be used any time at the discretion of the investigator.

COVID-19 vaccines (except for live attenuated vaccines for COVID-19) are permitted during the study. If administered, COVID-19 vaccines should not be administered on the same day as any of the study medications; please discuss with the Medical Monitor regarding the timing of COVID-19 vaccine administration during this study.

3.6.1 Prohibited Medications or Treatments

Subjects must be instructed not to take any medications, including over-the-counter products without first consulting with the investigator. The following medications are prohibited during the study:

- Any investigational anti-cancer therapy not described in this protocol
- Any concurrent therapy for anticancer intent (other than study medications), including radiotherapy (except palliative radiotherapy after consultation with the Sponsor Medical Monitor), or systemic therapy including chemotherapy, hormonal or hormonal suppression therapy, immunotherapy, or biologic therapy.
- Steroid and immunosuppressive medication usage: data indicate that corticosteroids have an adverse effect on T cell function and that they inhibit and damage lymphocytes [Schleimer, 1984]. Furthermore, as with all immunotherapies intended to augment cell-mediated immunity, there is a risk that concomitant immunosuppressives such as

steroids will counteract the intended benefit of the proposed SL-172154 therapy. Therefore, the use of steroids during this trial is as follows:

- Therapeutic use: Subjects who require immunosuppressive medications (e.g., corticosteroids) for management of irAE or IRRs that the investigator assesses as possibly related or related to SL-172154 should be managed per Toxicity Management Guidelines in Section 3.7.1.1.
- Steroid premedication for CT-contrast allergies is permitted.
- Steroid premedication prior to each dose of MIRV administration and SL-172154 administration for IRR prophylaxis is permitted.
- Primary prophylactic use of steroids for nausea/vomiting is not permitted.
- Non-steroidal, systemic immunosuppressive medications are not permitted.
- If steroids are required for managing any specific conditions, please contact the Medical Monitor.
- **[MIRV Cohort]** Folate-containing supplements
- Live attenuated vaccines (including live attenuated vaccines for COVID-19) during the study and through 30 days after the last dose of SL-172154.

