Grade 3	
• Interrupt SL-172154
○ Permanently discontinue SL-172154 if CRS does not resolve within 72 hours with management.• Vital signs should be measured approximately every 15 minutes for the first hour after discontinuation of SL-172154 infusion and then approximately every 30 minutes for the second hour.• Hospitalization required for close monitoring and management of symptoms related to organ dysfunction.• Monitor subjects with continuous cardiac telemetry and pulse oximetry. Consider performing an ECHO/MUGA to assess cardiac function.• Treat hypotension with IV fluid for blood pressure support and/or pressers. Cryoprecipitate or fresh frozen plasma may be required for coagulopathy. Manage per institutional guidelines.• Implement additional management per institutional standards (e.g., epinephrine, diphenhydramine, famotidine or other available H2 receptor antagonist, corticosteroids, bronchodilators, oxygen, fluids, meperidine for rigors, etc.). Epinephrine is the drug of choice in an anaphylactic reaction and its administration should not be delayed.• Administer tocilizumab as per your institutional guidelines and local label.• Second-line therapies to be considered:
○ Methylprednisolone 2 mg/kg/day IV. If corticosteroids are initiated, continue corticosteroids for at least 3 doses or until complete resolution of symptoms, and consider corticosteroid taper. For subjects with severe neurologic symptoms, consider using dexamethasone due to more efficient penetration of the blood-brain barrier.○ anti-TNF-α mAbs (infliximab) or soluble TNF-α receptor (etanercept), or IL-1R-based inhibitors (anakinra). 
Resume SL-172154 at one dose level lower only when all symptoms/ clinical features of CRS resolve within 72 hours and follow the guidelines below:
 
• Subjects who experience Grade 3 CRS should be hospitalized for the next two subsequent infusions of SL-172154. Subjects should be under prolonged observation for a minimum of 12 hours after the completion of the infusion.• For all subsequent infusions, infuse SL-172154 at least at twice the infusion time. If no recurrence of symptoms, subsequent infusions can be performed in an outpatient setting.• Premedicate with dexamethasone 20 mg, antipyretic, antihistamines (H1/H2 inhibitors), and manage per institutional guidelines.• If Grade 3 CRS recurs, permanently discontinue SL-172154.

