	
 • If persistent or rising liver chemistries, or significant clinical symptoms and an immune etiology is suspected, start oral prednisone 0.5 to 1 mg/kg/day (or equivalent of methylprednisolone) with 4-week taper. Obtain hepatology consult and assessments as above, monitor liver function daily; consider liver biopsy. • After careful consultation with hepatology, consider resuming SL-172154 at one dose level lower when toxicity \leq Grade 1 and corticosteroid taper to \leq 10 mg/day prednisone or equivalent.
Grade 4	
 • Permanently discontinue SL-172154. • Consider hospitalization; obtain hepatology consult; assessments as above; monitor liver function daily; consider liver biopsy. • If an immune etiology is suspected, immediately start methylprednisolone 1 to 2 mg/kg (start with 2 mg/kg for Grade 4) or equivalent. If refractory after 3 days, consider mycophenolate mofetil (MMF). Avoid the use of infliximab in immune mediated hepatitis.

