5.1.4 Monitoring Dose Administration

SL-172154 must be administered in an outpatient oncology treatment center or inpatient unit to enable close monitoring of subjects and proactive management of AEs. The risks associated with administration of SL-172154 include infusion reactions and CRS as described in Section [1.7.1](#). Therefore, appropriate drugs and medical equipment to treat acute HSRs and monitoring and management of CRS must be immediately available, and study personnel must be trained to recognize and treat these toxicities. In case an event of CRS should occur, ensure that at least 2 doses of tocilizumab are available prior to each infusion of SL-172154 (see Section [3.7.1.2](#) for toxicity management recommendations). When tocilizumab is not available, consider using drug with similar mechanism of actions such as anti-IL-6 receptor monoclonal antibodies (e.g., sarilumab) or anti-IL-6 mAbs (e.g., siltuximab).

Subjects will be monitored prior to, during, and after the completion of each SL-172154 infusion. Vital signs will be measured as outlined in the SOA in Section 6.1 and Section 6.2; vital signs may also be measured at other timepoints as clinically indicated.

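### Section 3.6.1 bars non-steroidal systemic immunosuppressants with no allowance for CRS, while Section 3.7.1.2 instructs tocilizumab at CRS Grades 3 and 4

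*Protocol*

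**What the plan says.** Protocol Section 3.6 allows supportive care subject to the prohibited list in 3.6.1. That list has a bullet on steroid and immunosuppressive use. After a rationale about counteracting SL-172154, the bullet introduces its sub-list with "Therefore, the use of steroids during this trial is as follows". Two entries in the sub-list matter here:

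- An allowance for "Subjects who require immunosuppressive medications (e.g., corticosteroids) for management of irAE or IRRs" judged related or possibly related to SL-172154, who "should be managed per Toxicity Management Guidelines in Section 3.7.1.1".
- The flat line "Non-steroidal, systemic immunosuppressive medications are not permitted".

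The toxicity sections read differently. Section 3.7.1.2, for Grade 3 CRS, says "Administer tocilizumab as per your institutional guidelines and local label", and Grade 4 carries an equivalent instruction. Section 3.7.1.3, for Grade 4 hepatotoxicity of suspected immune cause, says "If refractory after 3 days, consider mycophenolate mofetil (MMF)". Section 5.1.4 tells sites to "ensure that at least 2 doses of tocilizumab are available prior to each infusion of SL-172154".

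Section 3.7 describes the toxicity guidelines as non-prescriptive and leaves room for clinical judgement.

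**The concern.** Taken at face value, the prohibited list and the CRS table give a site opposite answers on tocilizumab. The event concerned is one that Section 3.7.1.2 itself describes as potentially fatal.

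Two things are at stake. The first is clarity for the site while it is treating the event. The second is the record: Protocol Section 14.4 defines a deviation as any noncompliance with the protocol, to be reported to the sponsor and sent to the IRB/IEC under its guidelines. SAP Section 6.2 then summarises deviations by type and subtype and as major or minor. If sites or monitors read the conflict differently, the same treatment could be a deviation at one site and compliant care at another.

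**Working it through.** No arithmetic applies. The check sets the passages side by side, agent by agent.

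| Agent and setting | Under 3.6.1 | Inside the irAE/IRR allowance? | In the toxicity section | Result |
|---|---|---|---|---|
| Tocilizumab, CRS Grades 3 and 4 | Barred | No, CRS not named | To be given (3.7.1.2) | Direct contradiction |
| Tocilizumab, CRS Grade 2 | Barred | No | To be considered if signs persist after interruption and corticosteroids (3.7.1.2) | Conflict, optional use |
| Infliximab, etanercept, anakinra, CRS Grades 3 and 4 | Barred | No | Second line, to be considered (3.7.1.2) | Conflict, optional use |
| Mycophenolate, Grade 4 hepatotoxicity, suspected immune cause, refractory | Barred by the flat line | Arguably yes, as an irAE | To be considered (3.7.1.3) | Ambiguous |

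Four steps support the table.

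1. **Can CRS be read into the allowance?** Not from its words. The protocol gives CRS its own section (3.7.1.2) and its own grading system (ASTCT), apart from IRRs (3.7.1.1). Section 1.7.1 lists irAEs as a separate risk from IRRs and CRS.
2. **Does the cited section help?** Section 3.7.1.1 covers IRRs. Its treatment lists include corticosteroids but no non-steroidal immunosuppressant, so following the pointer does not lead to permission for any agent in the table.
3. **Is there another route?** The Medical Monitor contact line in 3.6.1 concerns steroids only. Section 6 says that waivers and exemptions are not allowed.
4. **How far does the instruction reach?** Section 3.7.1.2 sends some Grade 2 subjects (older, with extensive comorbidity, or worsening) to Grade 3 management, so the instruction can apply to them too. The availability requirement in 3.7.1.2 and 5.1.4 applies before infusion for every subject in both regimens.

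**The case against.** The strongest reply is that the intent is plain and the defect is editorial. Section 1.7.1 uses the title Toxicity Management Guidelines for Section 3.7.1 as a whole and says that it covers both IRRs and CRS. The 3.7.1.1 pointer is therefore probably a slip for 3.7.1, since an IRR table could not govern the irAEs that the bullet names. Read that way, the pointer reaches the CRS and hepatotoxicity tables. The prohibition also sits in a list introduced as rules on steroids, and a site told to stock tocilizumab will expect to use it. Following 3.7.1.2 is itself following the protocol, and SAP 6.2 defines no prohibited-medication category.

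Much of this stands. It makes it likely that sites would act on the CRS table, and it means that a deviation is possible rather than certain. It does not remove the conflict. Even with the pointer corrected, the allowance does not name CRS. The flat line expressly addresses non-steroidal agents, under a parent bullet that covers immunosuppressives generally. No text says that the specific section overrides the general one, and non-prescriptive guidance does not clearly displace a prohibition.

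Two stronger readings are tempting, and the documents do not support them:

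- **That every agent is both prohibited and instructed.** Only tocilizumab at CRS Grades 3 and 4 is instructed. The others are to be considered, and mycophenolate may fall within the irAE allowance.
- **That the conflict alters the DLT count**, because Grade 3 CRS unresolved at 72 hours forces permanent discontinuation, itself a DLT criterion. Under Section 3.5 any related or possibly related Grade 3 or higher AE in the DLT window is a DLT unless excepted, and CRS is not among the exceptions. Such an event is already a DLT, however quickly it resolves.

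**Conclusion.** The contradiction is real and narrow. Tocilizumab for CRS Grades 3 and 4 is barred by the wording of 3.6.1 and instructed by 3.7.1.2. Tocilizumab at Grade 2 and the second-line CRS agents conflict with 3.6.1 as optional treatments. Mycophenolate is an ambiguity caused mainly by the misdirected cross-reference. How such use would appear in the SAP 6.2 tables is unclear.

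This rests on one assumption: that these agents fall within the class named in 3.6.1, which the protocol does not define.

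The size cannot be given as a number. A reader might take the absence of CRS in SL03-OHD-101 and derive an upper bound on affected subjects. However, Section 1.4.7 dates the no-CRS statement 23 April 2022 and the count of 26 subjects 12 September 2022. Section 1.7.1 only partly bridges the gap, by saying that the IRRs were not consistent with CRS. Those data also concern CRS of any grade on monotherapy, not Grades 3 and 4 on a combination.

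No estimand, sample size, analysis or decision rule is affected. This should be fixed because it concerns rescue for a named serious risk. It is a contradiction in safety text, not a design choice.

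**What to change.** The sponsor should:

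- Reconcile Section 3.6.1 with 3.7.1.2, 3.7.1.3 and 5.1.4 so that no treatment is both prohibited and called for. Which clinical rule stands is for the sponsor's medical team, and this review takes no view on it.
- Correct the 3.7.1.1 cross-reference in the therapeutic-use bullet so that it points to the sections that govern irAEs, CRS and hepatotoxicity.
- Make the deviation classification follow from the reconciled text, so that SAP Section 6.2 treats the same use the same way at every site.

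The cost is one or two sentences in an amendment or clarification memo, with a matching line for deviation handling. No subjects, procedures or data are added.

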3.6.2 Medications to be used with Caution

Please refer to the current listing of drugs that are cytochrome P450 (CYP450) substrates, including CYP3A4, CYP2D6 and P-glycoprotein (P-gp) substrates, at: <https://www.fda.gov/drugs/drug-interactions-labeling/drug-development-and-drug-interactions-table-substrates-inhibitors-and-inducers#table3-1>.

SL-172154

SL-172154 is a therapeutic protein that may induce the transient release of cytokines including IL-6 which in turn, may inhibit the activity of CYP450 enzymes including CYP3A4 activity [Evers, 2013]. Although not tested clinically, a drug-drug interaction may occur with the co-administration of medications that are CYP450 substrates. Drugs metabolized by CYP450 enzymes may have reduced clearance or an increase in half-life or peak plasma concentration and should be used with caution. There may be an increased risk of side effects for drugs that are CYP450 substrates. Where possible consider substitutions for these medicinal products if therapeutic effects cannot be monitored.

PLD

Doxorubicin is a major substrate of CYP3A4 and CYP2D6, and P-gp. Clinically significant interactions have been reported with inhibitors of CYP3A4 (e.g., ketoconazole, erythromycin, ciprofloxin), CYP2D6 (e.g., paroxetine, fluoxetine, and/or P-gp (e.g., verapamil), resulting in increased concentration and clinical effect of doxorubicin.

Inducers of CYP3A4 (e.g., phenobarbital, phenytoin, St. John's Wort) and P-gp inducers may decrease the concentration of doxorubicin. If possible, avoid concurrent use of doxorubicin with strong inhibitors and strong inducers of CYP3A4, CYP2D6, or P-gp.

MIRV

In vitro metabolism studies demonstrated that DM4 is predominantly metabolized by thiol s-methyltransferase to form S-methyl DM4, which is further metabolized into sulfoxide methyl-DM4. As S-methyl DM4 has been shown to be primarily metabolized by CYP3A, its exposure could potentially be increased in the presence of strong CYP3A inhibitors. Drinking greater than one serving (250 mL) of grapefruit juice per day should be avoided.

Both DM4 and S-methyl DM4 are substrates for MDR1 efflux transporter. Their exposure could potentially increase in the presence of MDR1 efflux transporter. *In vitro* metabolism data also indicates that DM4 is a time-dependent inhibitor of CYP3A4. The risk of a significant *in vivo* drug-drug interaction caused by inhibition of CYP3A4 or MDR1 is unknown. Treatment of patients with concomitant medications that are inhibitors of MDR1, sensitive substrates of CYP3A or are CYP3A substrates with a narrow therapeutic index should be used with caution and carefully monitored. Please consult with the Medical Monitor if further guidance is needed.

